Appendix E. Details for Analysis with a Synthetic Placebo Arm

E1. Historical Data Selection

The historical data are carefully selected based on the similarity in target population, entry criteria, prior and concomitant medications, central review of endoscopies and years conducted between historical trials and Study M15-722. Subject-level historical placebo data consists of subjects from two recent AbbVie clinical trials with similar populations (Bio-IR), entry criteria and study designs: upadacitinib phase 2b/3 Study M14-234 Substudy 1 and Substudy 2. All bio-IR placebo subjects from M14-234 Substudy 1 and Substudy 2 will be identified.

E2. Propensity Score Estimation

Propensity score method will be used to balance the population-level baseline characteristics between in trial data and historical placebo group. In order to calculate propensity scores, selected common baseline demographics and characteristics variables among Study M15-722 and the two historical Studies M14-234 Substudy 1 and Substudy 2 bio-IR will be used as covariates in propensity score estimation.

Main baseline demographic characteristics can include:

- age (years)*,
- weight (kg)*,
- body mass index (BMI) (kg/ m²).
- sex (male, female)*,
- ethnicity (Hispanic or Latino, not Hispanic or Latino)
- race (white, non-white),
- region (Europe, North America, or rest of world),
- tobacco user (current, former, never, unknown),
- alcohol user (current, former, never, unknown).

* indicating those demographic characteristics must be included.

Main baseline disease characteristics can include

- adapted Mayo score*,
- hs-CRP (mg/L),
- fecal calprotectin (mg/kg),
- albumin (g/L),
- UC disease duration in years,
- UCEIS,
- Geboes score,
- baseline steroid use (yes, no)*,
- baseline immunosuppressant use (yes, no)*,
- baseline aminosalicylates use (yes, no),
- prior exposure to biologic/JAK therapy for UC (1, >1)
- prior exposure to anti-TNF use for UC (yes, no),
- mayo endoscopic subscore (2, 3)*,
- disease extent (left-sided, extensive/pancolitis, limited to rectum)*

* indicating those baseline disease characteristics must be included due to their clinical relevance. Other baseline characteristics (and their specific levels of categorical variables) will be assessed in model diagnostics if data does not allow large number of covariates when estimating propensity score.

Propensity score is the probability of a patient being assigned to a treatment instead of the other one conditional on a given set of baseline characteristics. It is determined by a logistic regression with selected above common baseline covariates. Overlap and balance of propensity score between the in-trial data and synthetic placebo control will be assessed using histogram and descriptive statistics.

Specifically, covariate balance will be checked between all subjects enrolled in Study M15-722 and historical placebo subjects from the two historical trials using standardized mean difference (SMDs) and a threshold of 0.1 for each of the baseline characteristics. To assess overall performance of different synthetic control algorithms, the mean of absolute SMDs across all baseline characteristics that are included in estimating propensity score is the main measure with smaller values indicating better balance. Considering the modest sample size in the current trial, sample size preservation in the matched patients is another key consideration in determining the final recommendation.

E3. Analysis using placebo synthetic control with propensity score matching

Propensity score matching method (Rosenbaum and Rubin, 1985) matches treatment patients with synthetic placebo subjects based on propensity scores such that matched treatment subjects and placebo subjects are comparable in terms of covariates used in propensity score determination. This process mimics randomization to create two comparable groups with a caution of limitation that the matching is conditional on included covariates.

A 1:1 matched placebo group will be generated from the above set of synthetic placebo subjects using greedy matching to match the treatment subjects in Study M15-722. We will start the matching with the optimal caliper 0.2, which was recommended by Austin (2011), with the intention to match 40 placebo subjects. Other caliper values or matching ratios may also be considered to improve balance and preserve sample size in matched patients. If multiple placebo subjects have propensity scores that are equally close to that of the treated subject, one of these untreated subjects will be selected at random. Subjects who are not selected in the matching process will be excluded from further analysis.

Following matching, baseline covariates will be summarized for subjects in Study M15-722 and matched historical placebo subjects to ensure balance is generally achieved.

[figure not shown]
The optimal matching will also be performed based on a distance measure, caliper, calculated from the propensity scores estimates.

E4. Implementation

To reduce operational bias and maintain study validity, the propensity score calculation and matching described in [Appendix E](#) will be conducted by an independent statistician who is removed from Study M15-722. Prior to the first dose of the 40th subject, the study team and the independent statistician will meet as needed and agree on the statistical details of each step above, with any question (must be unrelated to treatment assignment information and in trial and historical subjects outcome) from the independent statistician resolved during the meeting(s).

The process to implement the propensity score analysis is summarized in [Figure 4](#). Each step is described in detail below. These steps should happen after 40 subjects enrolled into Study M15-722 and prior to the primary database lock.

Figure 4. Flowchart of Implementation

1. Input baseline datasets of Study M15-722

A dataset of Study M15-722 containing study ID, de-identified subject IDs, and baseline characteristics will be delivered to the independent statistician by the study team. No post-baseline data should be contained in this dataset.

2. Input integrated baseline dataset of historical placebo subjects

A dataset integrating the baseline characteristics from the two studies with historical placebo subjects will be delivered to the independent statistician by the study team. No post-baseline data should be contained. In addition, study IDs and subject IDs in this dataset will be de-identified by the study programming team before delivering to the independent statistician.

3. Post-baseline dataset of historical placebo subjects

A dataset of historical placebo subjects integrating endoscopic improvement at Week 8 from Study M14-234 Substudy 1 and Substudy 2 will be generated. Subject ID will be included. This dataset is to be kept by study team for the final analysis and should not be accessible to the independent statistician.

4. Propensity score analysis and communication with study team

Prior to enrollment completion, the study team and the independent statistician will meet as needed and agree on the final propensity score analysis rules (for example, matching ratio, matching caliper) of each step. Any question (must be unrelated to treatment assignment information) from the independent statistician will also be addressed during these meeting(s).

After Study M15-722 enrolled 40 subjects, the input datasets will be delivered to the independent statistician for propensity score estimation and matching, without accessing the subject-level post-baseline data (including primary endpoint data) of selected historical placebo subjects and Study M15-722 subjects. The independent statistician will

check the covariate balance before and after matching is performed to make sure the balance is improved following the matching.

5. Final covariate datasets

The resultant datasets (matched) containing subject-level covariate data will be delivered by the independent statistician to the study team prior to the primary database lock for analysis. Matched datasets should discard those unmatched subjects. The analysis-ready datasets should include variables such as re-identified subject ID, baseline characteristics, propensity score.

There is no plan to share interim data with external experts or with Regulatory Agencies (prior to study completion and availability of final study results).

6. Final data analysis

After database lock, the study programming team will merge the final output datasets with datasets containing post-baseline data of ravaglimab and historical placebo subjects and perform the pre-specified analyses.

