Blood sampling, IV infusions, and subcutaneous SC injections can cause local bruising, inflammation, and pain. The preparation for endoscopy, and the endoscopy and biopsy procedure itself, although generally well tolerated, can be associated with diarrhea, abdominal pain, and in more severe cases, perforation, bleeding, effects from anesthetic medications, and infection.

In view of the coronavirus disease of 2019 (COVID-19) pandemic, the benefit-risk profile of various immunomodulatory therapies on COVID-19 is being evaluated. At this time, the effects of ravagalimab on the course of COVID-19 is not known.

The benefit-risk profile of ravagalimab is considered appropriate for an experimental therapy at this stage of clinical development in an especially refractory patient population.

Taken together, the data support further development of ravagalimab in Phase 2 for subjects with moderate to severe UC who have failed prior biologic therapy and/or tofacitinib. For further details, please see findings from completed studies, including safety data in the ravagalimab Investigator's Brochure.

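### Synthetic-control candidates are scored only on the covariates in their own propensity model, so imbalance on an omitted covariate does not count in the main measure

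*SAP*

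**What the plan says.** SAP 8.3.5 and Appendix E build a matched placebo group for the roughly 40 ravagalimab subjects from the Bio-IR placebo subjects of upadacitinib Study M14-234. The plan starts from 1:1 greedy matching with a caliper of 0.2. Other calipers and ratios are allowed, and optimal matching is a sensitivity analysis.

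Appendix E2 does not fix the covariates of the propensity model. Its disease list opens with "Main baseline disease characteristics can include", and the demographic list is permissive in the same way. Starred disease items are described as "indicating those baseline disease characteristics must be included due to their clinical relevance". For the unstarred items, E2 says only: "Other baseline characteristics (and their specific levels of categorical variables) will be assessed in model diagnostics if data does not allow large number of covariates". The two-level count listed as "prior exposure to biologic/JAK therapy for UC (1, >1") carries no star.

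To compare algorithms, E2 states that "the mean of absolute SMDs across all baseline characteristics that are included in estimating propensity score is the main measure", smaller being better. It then adds that "sample size preservation in the matched patients is another key consideration in determining the final recommendation".

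Four other provisions touch on balance:
- E2 sets an SMD threshold of 0.1 for each characteristic. It is worded for all enrolled subjects against the historical placebo subjects, and no consequence is stated.
- E3 summarises covariates after matching, with no numerical criterion.
- E3 cautions that matching is conditional on the covariates included.
- E4 has the independent statistician confirm that balance improved after matching.

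**The concern.** A balance score can rank candidates fairly only if every candidate is scored on the same items. Here the items are whatever each candidate put in its model, so a candidate that omits a poorly balanced covariate is not marked down for it. None of the four other provisions brings an omitted covariate into the choice or says what follows if it stays unbalanced.

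Prior-therapy count is a concrete case. SAP Table 5 lists M14-234 subjects as not previously treated with a JAK inhibitor, whereas M15-722 admits tofacitinib failures. Protocol 2.2 describes the benefit-risk as appropriate "at this stage of clinical development in an especially refractory patient population". The planned CMH tests stratify only on baseline steroid use and endoscopic subscore, so they would not adjust for a remaining difference in prior-therapy count.

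At stake are the confidence intervals and p-values of the matched-placebo comparisons for the primary, secondary and selected additional endpoints.

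**Working it through.** The SAP gives no figure for this measure, so there is none to reproduce.

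**1. Size of the list (Appendix E2).** There are 9 demographic items, 3 of them starred (age, weight, sex). There are 14 disease items, 5 of them starred (adapted Mayo score, steroid use, immunosuppressant use, endoscopic subscore, disease extent). In total 9 + 14 = 23 items, 3 + 5 = 8 mandatory and 15 optional. Extra factor levels (region +1, tobacco +2, alcohol +2, extent +1) give 23 + 6 = 29 model terms, of which 8 + 1 = 9 are mandatory.

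**2. Arithmetic of the measure.** Take K covariates, one at absolute SMD 0.60 and the rest at 0.10. The mean is [(K − 1) × 0.10 + 0.60] / K.
- K = 23: 2.8/23 = 0.122
- K = 15: 2.0/15 = 0.133
- K = 9: 1.4/9 = 0.156

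Leaving the bad covariate out of the model, with the others unchanged, gives 0.100 each time.

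**3. The 0.1 threshold as a guard.** With 40 against 40 under randomisation, SE(SMD) ≈ √(2/40) = 0.224. The expected absolute SMD is 0.224 × √(2/π) = 0.18, and P(absolute SMD < 0.1) = 2Φ(0.1/0.224) − 1 = 0.35. Even randomised groups would miss the threshold on about two covariates in three.

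**4. Simulation with one hard covariate.** Assumptions: 40 treated, 12 independent normal covariates, 11 of them shifted 0.15 SD and one shifted as shown. The score is a ridge logistic model in place of the Firth option, with greedy 1:1 matching, caliper 0.2, and 1000 runs per cell. The pool size is assumed. By subtraction 325 − 65 − 65 − 161 = 34 subjects come from the Phase 2b substudy, but the Phase 3 number is redacted. Pool 120, hard covariate kept v dropped:

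| Shift (SD) | SAP measure | Fixed list of 12 | Residual SMD, hard covariate | Matched pairs |
|---|---|---|---|---|
| 0.5 | 0.105 v 0.104 | 0.105 v 0.138 | 0.10 v 0.51 | 34.4 v 36.0 |
| 0.8 | 0.109 v 0.104 | 0.109 v 0.163 | 0.09 v 0.81 | 31.9 v 36.0 |
| 1.2 | 0.119 v 0.104 | 0.119 v 0.195 | 0.08 v 1.20 | 27.4 v 36.0 |

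Pools of 80 and 160 agree in direction. In single data sets the SAP measure was lower after dropping in 50–73% of runs. That is near a coin-flip for moderate imbalance and more often for large imbalance.

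**5. Simulation with three candidate models.** The candidates were mandatory covariates only, mandatory plus prior-therapy count, and all covariates. More than one prior therapy was assumed in 65% of treated and 46% of pool subjects. That is an SMD of 0.19/√[(0.65 × 0.35 + 0.46 × 0.54)/2] = 0.39. Across runs, an absolute SMD above 0.25 on that covariate remained in 27–34% of data sets under the SAP measure and 5–13% under a fixed list. The mandatory-only model left 0.36–0.37; adding the one term gave 0.09.

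**6. One covariate set, caliper varied from 0.1 to 0.5.** Residual SMD on prior-therapy count, SAP measure v full-list measure: 0.407 v 0.398 with the 9 mandatory terms, and 0.085 v 0.086 with prior-therapy count added. The wording then makes almost no difference.

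**7. Scale of bias.** With assumed odds ratios of 0.4 (more than one prior therapy), 0.7 per SD (CRP) and 1.4 per SD (albumin), the bias in the matched placebo rate was 1.3–1.5 points, against about 0.1 with a fixed list, on a true 6.1%. On 40 subjects that is 0.5–0.6 of a responder. The sampling SE is √(0.061 × 0.939/40) = 3.8 points.

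**The case against.** The strongest reply is that the measure was never meant to choose covariates. The alternatives the SAP names are greedy or optimal matching, calipers and ratios, and covariate reduction has its own trigger in E2. If the covariate set is settled beforehand, every candidate is scored on the same items and step 6 shows nothing to correct. This stands as a limit. The text, however, does not say that the set is settled beforehand, and it ties the score to the included covariates.

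A reader might infer that the rule is strongly biased towards small models, since it chose a reduced model in 74–81% of data sets in the three-candidate simulation. That figure does not show it. Two of the three candidates were reduced, so indifference alone gives 67%, and reduced models won 71–80% of the time with no imbalance at all. The residual imbalance in step 5 is the better evidence.

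The safeguards deserve credit. Eight covariates cannot be dropped, an independent statistician checks balance, and the matching rules are agreed without outcome data. A reader might suspect outcome-driven selection; the E4 procedure is designed to exclude it. What the safeguards lack is a rule for an omitted covariate.

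That prior-therapy count is prognostic is a clinical judgement, and the SAP chose its stars for clinical relevance. Table 5 supports only that a difference is foreseeable.

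**Conclusion.** The concern holds where candidates differ in covariate set: they are then scored on different lists, and an omitted covariate carries no weight in the main measure. The second consideration, matched sample size, pushed the same way on average in step 4. If all candidates share one set, the effect is close to nil.

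A reader might infer that the trial's main result is at risk. It is not: SAP 8.3.3 compares ravagalimab with a meta-analytic placebo prior and uses no matching. The reach is the additional matched-placebo analyses in 8.3.5, 8.4 and 8.5, in a proof-of-concept study without multiplicity control.

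The size of any bias rests on assumed pool sizes, shifts and odds ratios, and is probably modest beside the 3.8-point SE and the 25-point difference in SAP 2.4. Its direction is unknown, because it depends on which study has the more refractory subjects. This is a cheap improvement, not a flaw that invalidates the analysis.

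**What to change.** In SAP E2, compute the mean absolute SMD in the matched, analysed subjects over one fixed list of all 23 E2 characteristics. Use that list for every algorithm compared, whether or not a characteristic is in the propensity model, and report the maximum beside the mean. Keep matched sample size as the second consideration. Star the count of prior biologic/JAK therapies (1, >1) as mandatory; it adds one model term. Settle this before the first dose of the 40th subject, when E4 has the matching details agreed.

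The cost is a wording change, since these are baseline characteristics that E4 already plans to send to the independent statistician. Reported balance will look worse. Starring the one covariate costs about one matched pair (0.5–1.5 in simulation). If the new measure leads to the full 29-term model, the loss could be roughly 6–10 pairs under the assumed shifts. One set of runs gave 37.4 − 28.4 = 9.0 (pool 150) and 35.1 − 23.9 = 11.2 (pool 100). That loss should be weighed under the existing sample-size consideration; the fixed list does not oblige the team to adopt the full model.
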